PROTOCOL

Title of research programme: Clinical study on the prevention and treatment of postoperative metastasis in stage II A-III A lung cancer with negative expression of driver genes by Fuzheng Quxie Recipe

Research organization: Shanghai Municipal Hospital of Traditional Chinese Medicine

Principal Investigator: [name]

Version No.: 1.0, 2022.12.21

Efficacy of Fuzheng Quxie Formula for inhibiting metastasis after surgery in stage IIA-IIIA lung cancer with negative driver genes: study protocol for a multi-centre, double-blind, randomized controlled trial

Abstract:

Background: Metastasis is the main reason for poor prognosis and high mortality of lung cancer. Surgery and postoperative adjuvant chemotherapy are the first choice for patients with driver-negative stage I to IIIA lung cancer. However, the incidence of postoperative recurrence and metastasis did not significantly decrease. In China, traditional Chinese medicine (TCM) is commonly used to treat cancer. TCM has the potential to be used as an adjuvant therapy for lung cancer to reduce treatment related toxicity and improve clinical efficacy. In view of the positive results of the basic study of Fuzheng Quxie Formula against lung cancer metastasis, we plan to evaluate the efficacy of Fuzheng Quxie Formula against postoperative metastasis of stage IIA-IIIA lung cancer that is negative for driver gene expression.

Methods: A multi-centre, double-blind, randomised, placebo-controlled parallel group controlled trial will be conducted. Eligible patients will be randomised into a treatment group (daily Fuzheng Quxie Formula granules + regular chemotherapy) and a control group (daily Chinese medicine placebo granules + regular chemotherapy) in a ratio of 1:1. It is recommended that the participants' chemotherapy be used strictly in accordance with the dosage, duration and usage as recommended in the respective instructions and National Comprehensive Cancer Network (NCCN) guidelines. Fuzheng Quxie Formula was administered orally, twice a day, in the morning and evening, for 6 months. Follow-up after the end of medication, follow-up period of 3 years. After the end of the programme, follow-up was continued until 5 years or until the subject died (or progressed). The primary outcome was disease-free survival (DFS), and the secondary outcomes were overall survival (OS), minimal residual disease (MRD), circulating tumour cells detection, TCM symptom score, assessment of quality of life (QoL), immune indices, tumour markers, peripheral blood systemic immune- inflammation index (SII), prognostic nutritional index (PIN) and prognostic nutritional index (PNI).

Discussion: This will be the first trial to evaluate the efficacy and safety of Fuzheng Quxie Formula in inhibiting metastasis after surgery in stage IIA-IIIA lung cancer with negative driver genes. The results of this randomised controlled trial will fill a gap in this study by showing whether Fuzheng Quxie Formula combined with postoperative chemotherapy improves the prognosis for patients with lung cancer.

Ethics and Dissemination: The Ethics Committee of Shanghai Municipal Hospital of Traditional Chinese Medicine, Shanghai University of Traditional Chinese Medicine approved the study protocol (approval no.: 2023SHL-KY-19-01, 2023/02/23). The study will also be supervised and

managed by the Ethics Committee.

Keywords : Fuzheng Quxie Formula, Lung cancer in stage IIA-IIIA, Negative driver genes, Metastasis after surgery

Background

Lung cancer is one of the most common malignant tumours of respiratory system, with the mortality rate perennially ranking first among all kinds of malignant tumours, which greatly threatens the safety of human life^[1]. In developed countries (such as the United States), lung cancer is still the malignant tumour with the highest number of deaths^[2]. In China, the latest data shows that there are about 787,000 new cases of lung cancer, with an incidence rate of 57.26/100,000, ranking first in the national morbidity and cause of death by gender, causing economic losses of up to 221.4 billion, and this economic and social pressure will continue to increase^[3]. In recent years, due to the rapid advances in therapeutic modalities (e.g., molecular targeted therapy, immunotherapy, etc.), the survival time of lung cancer has been extended, but the 5-year survival rate of lung cancer still persists at a low level^[4]. Distal metastasis is the main cause of death in 90% of patients and there is a lack of effective treatment options^[5]. Surgery is currently the first choice for patients with stage I to IIIA lung cancer, but metastasis after radical lung cancer surgery is a bottleneck limiting its overall efficacy.

Currently, domestic and international guidelines related to lung cancer diagnosis and treatment recommend that patients with stage IB (high-risk type) need to undergo postoperative conventional chemotherapy, and that patients with stage IIA and IIIA must undergo conventional chemotherapy after surgery^[6]. However, only about 5% of lung cancer patients have long-term survival benefit^[7]. Studies have confirmed that the recurrence rate of patients with stage I lung cancer after adjuvant chemotherapy is around 17.8%, and about 45.5% of patients with stage II-III lung cancer may have recurrent metastasis. Among them, patients with stage I recurrence include : 63% are local recurrence, 40.5% are distant recurrence and 72% are new primary lung cancer^[8]. Wang Zezhou et al followed up the survival of 7753 patients operated for lung cancer and confirmed that the 5-year survival rates of patients with stage IB, IIA, IIB, IIIA and IIIB lung cancer were 78.5%, 78.2%, 62.9%, 49.3% and 33.0%, respectively. Therefore, standard chemotherapy administered after surgery presents an overall poor role in the prevention of recurrent metastasis in patients after radical lung cancer surgery. There is a need to develop new diagnostic and therapeutic protocols.

With the development of molecular targeted therapy and immunotherapy, patients with intermediate and advanced lung cancer who are positive for driver genes or have high PD-L1 expression can further benefit from targeted therapy or immunotherapy. Adenocarcinoma and squamous carcinoma are common pathologies in lung cancer. A study that included 371 Chinese lung cancer cases showed that the mutation types in lung adenocarcinoma were EGFR (60%), TP53 (57%), KRAS (13%), PIK3CA (7%), and ALK (7%), whereas those in squamous lung carcinoma included TP53 (87%), PIK3CA (43%), CDKN2A (20%), KMT2D (20%), and EGFR (17%) mutations^[9]. For ALK/EGFR/ KRAS/ROS1/MET mutations, there are Several targeted therapeutic agents have been approved, marketed internationally and in the health insurance. Wu Yilong et al. conducted a clinical study confirming the benefit of ositinib in patients after radical surgery for stage IB~IIIA lung cancer with driver gene EGFR positivity^[9, 10]. Meanwhile, immunotherapy sequential treatment after chemotherapy for Radical resection of lung cancer

patients with stage IB-IIIA lung cancer with high PD-1/L1 expression ($\geq 1\%$) may also provide a survival benefit and reduce the rate of metastasis. In addition, a study included 328 patients after resection of stage IA-IIB non-small cell lung cancer (NSCLC) to examine their immune checkpoint expression^[11]. The study showed that 62.0% (160/258) of the lung adenocarcinoma group had PD-L1 <1%, and only 38.0% (98/258) had PD-L1 $\geq 1\%$, suggesting that the expression of immune checkpoints is low in lung adenocarcinoma patients^[12]. Therefore, for patients with positive driver gene and high immune checkpoint expression after radical lung cancer surgery, standardised diagnostic and treatment protocols that can benefit patients clinically are already available. However, for patients with negative genes expression and low PD-1/L1 expression ($\leq 1\%$) after radical lung adenocarcinoma surgery, who have poor chemotherapeutic efficacy in the clinic and lack indications for molecularly-targeted or immunotherapeutic treatments, the development of effective, scalable and specific therapeutic protocols is urgently needed.

In summary, the existing multidisciplinary treatments available for lung cancer metastasis, such as chemotherapy, targeted therapy, and immunotherapy, have been developed based on alterations to the genetic structure and function of the tumour cells themselves in the primary foci. However, as tumour metastasis is often trans-organic and involves imbalances in the function of multiple systems, the overall efficiency of current strategies for the prevention and treatment of lung cancer metastasis is poor^[15]. TCM, which stresses the holistic concept and dialectical treatment, and committing to a people-centered approach, has unique advantages in preventing and treating tumour metastasis^[13-15]. A large number of basic and clinical studies have confirmed that TCM can significantly inhibit the metastasis of lung cancer, significantly prolong the survival period of patients, and improve their quality of life^[16, 17]. Therefore, it is an important breakthrough to overcome the bottleneck of tumour metastasis in clinic under the holistic view and syndrome differentiation of TCM to understand the pathogenesis of lung cancer metastasis from a systemic perspective, and then anchoring the key therapeutic targets to develop effective prevention and treatment strategies^[18-20].

[name] group focuses on lung cancer metastasis research. Under the guidance of a master of Chinese medicine [name]'s academic idea of "treating cancer by reinforcing healthy qi", and incorporating Lao Zi's "Existence and non-existence give birth the one to the other", modern oncology and immunology, the team suggests the core pathogenesis of cancer metastasis in the subclinical stage of cancer --"Deficiency of Vital Qi and Hidden Toxin" theory. According to the theory, immune disorders caused by immune senescence and immune escape are "Deficiency of Vital Qi", while circulating tumour cells, quiescent cancer cells and tumour stem cells are the modern biological connotations of "toxicity". The residual cancer cells after radical treatment of lung cancer are the "Hidden Toxin". After radical lung cancer surgery, residual cancer cells (hidden toxin) are latent in the body and in dormant or quiescent stage. When there is a deficiency of vital qi, the efficiency of immune surveillance and immune clearance decreases, and the cancer cells go from the quiescent phase to the proliferative phase, leading to the occurrence of tumour metastasis. The team further found that myeloid-derived suppressor cells, regulatory T cells, and circulating tumour cells ("hidden toxin") are important factors in the subclinical state of lung cancer metastasis in clinical studies, and analysed their expression patterns^[21]. The team took the lead in establishing the world's first human lung adenocarcinoma circulating tumour cell line (CTC-TJH-01), as well as a platform for metastasis-specific studies of lung cancer^[22].

Under the theory of "Deficiency of Vital Qi and Hidden Toxin", the group established the treatment method of "supporting vital qi" and "dispelling hidden toxin", and created a Chinese medicine formula for inhibiting postoperative metastasis of early- and middle-stage non-small cell lung cancer. In this formula, Sheng Huang Qi, Fu Ling, Bai Zhu tonify spleen and stomach to "strengthen earth to generate metal"; Bei Sha Shen, Tian Dong, Mai Dong nourishes yin and moistens the lungs; Hai Zao, Xia Ku Cao, Kun Bu, which soften and resolve hard mass, and Bai Hua She She Cao, Shi Jian Chaun, Shi Shang Bai, which clear heat, detoxifying to disperse nodules. Through in-depth clinical and basic research, the team has obtained the scientific basis for Fuzheng Quxie Formula to inhibit metastasis: (i) Fuzheng Quxie Formula has the clinical effect of preventing recurrence and metastasis: the team, in cooperation with Shanghai Lung Hospital, carried out a prospective clinical study, which confirms that the DFS rates of early and middle stage NSCLC patients after intervention with Fuzheng Quxie Formula were 98.8% and 96.5% in 1 and 2 years, respectively, which were higher than 95.3% of the patients in the pure follow up group. (ii) The mechanism of inhibiting metastasis by Fuzheng Quxie Formula may be to regulate the immune function to promote apoptosis of circulating tumour cells: intra-group comparison of immune indexes before and after the study suggests that the peripheral blood NK, CD3+ and IgM content of the treatment group after intervention of Fuzheng Quxie Formula increased significantly ($P < 0.01$), and at the same time, it can reduce the number of circulating tumour cells in the blood ($P < 0.01$), suggesting that Fuzheng Quxie Formula has the tendency to regulate patients' immunity and inhibit circulating tumour cells to control tumour progression; (iii) Mechanism study found that Fuzheng Quxie Formula can improve immune function and restore the state of body immune balance: Fuzheng Quxie Formula can up-regulate the expression of positive immune cells, such as NK cells and T-cell subpopulations, which have an inhibitory and killing effect on tumour cells, and down-regulate positive immune cell expressions, which promote tumour cell proliferation, metastasis, immune escape, and so forth, Down-regulate the expression of negative immune cells such as myeloid-derived suppressor cells and regulatory T cells, which promote the proliferation, metastasis and immune escape of tumour cells; inhibit and remove circulating tumour cells in the peripheral circulation; and influence and regulate the metabolic reprogramming of tumour cells in terms of sugar, fat and amino acids. Meanwhile, the theory of "Deficiency of Vital Qi and Hidden Toxin" guided the construction of clinical efficacy prediction and metastasis risk assessment model for TCM treatment of lung cancer (Journal of Traditional Chinese Medicine, 2022), which found that maintaining peripheral immune homeostasis is an important basis for TCM to inhibit lung cancer metastasis, and optimised and enriched the prognostic assessment system of lung cancer. Fuzheng Quxie Formula has been applied as an in-hospital preparation for many years, and has successfully entered the process of joint development of new drugs with enterprises.

Therefore, in response to the urgent clinical needs of postoperative patients with IIA-IIIA non-small cell lung cancer who are negative for driver gene expression, we attempted to objectively evaluate the efficacy of Fuzheng Quxie Formula in inhibiting metastasis of IIA-IIIA non-small cell lung cancer who are negative for driver gene expression, and to actively explore the establishment of a combined prevention and treatment programme of TCM and Western medicine by designing a clinical study protocol in line with the international norms.

1 Methods

1.2 Study Population and Eligibility Criteria

The sources of cases for this study were inpatients and outpatients admitted from 1 July 2022 to 30 June 2025 with negative expression of driver genes in postoperative stage IIA-IIIA lung adenocarcinomas with qi and yin deficiency. Inclusion for observation should be no later than 6 weeks postoperatively. Screening will be based on inclusion and exclusion criteria (Table 1).

Table 1. Study Inclusion and Exclusion Criteria.

Inclusion criteria	Exclusion criteria

① Patients with clinical staging of stage IIA-IIIA lung adenocarcinoma after radical surgery, patients within 6 weeks after surgery;
 
② Driver gene negative (no EGFR, ALK, ROS1 mutations), PD-1/L1 expression <1%;
 
③ Fulfilling the diagnostic criteria for the lung qi and yin deficiency type, the primary symptoms are cough, low sputum, shortness of breath, low or muffled voice, weakness, and thirst without wanting to drink. Secondary symptoms include spontaneous sweating, nocturnal sweating, five heartburns, red tongue or teeth marks on the sides of the tongue, and a weak pulse. At least two primary symptoms and one of the secondary symptoms are present;
 
④ Patients aged between 18 and 75 years;
 
⑤ Patients with basically normal blood and biochemical indicators, without serious viral or bacterial infections; without organ failure and serious
	
① Patients with incomplete resection or whose cancer has undergone recurrence or metastasis;
 
② Patients who are being treated with other drugs or therapies (including other Chinese herbal medicines, immunological drugs, radiotherapy, etc.);
 
③ Patients who are themselves mentally ill and have a lack of autonomous behaviour;
 
④ Women who are pregnant, preparing for pregnancy or breastfeeding;
 
⑤ Combined heart, lung, brain, liver, kidney and haematopoietic system and other serious diseases, psychiatric patients;
 
⑥ Allergic or known hypersensitivity to the components of the drug;
 
⑦ Patients who are participating in other clinical trials or have participated in other clinical trials within 3 months;
 
⑧ Alcohol and/or psychoactive substances abuse, drug

heart disease (TBIL <68 μ mol/L, AST <90 IU/L, CREA <350 μ mol/L, WBC >3.5 \times 10 ⁹ /L and < 12 \times 10 ⁹ /L, PLT >80 \times 10 ⁹ /L, HCT >0.20)	abusers and dependent persons;
⑥ Those with a tumour PS score \leq 2 and no other serious comorbidities;	⑨ Other pathologies or conditions that, in the judgement of the investigator, have the effect of reducing the likelihood of enrolment or complicating enrolment, e.g., frequent changes in the work environment, unstable living conditions, and other conditions that predispose to loss of visits.
⑦ The patients themselves gave informed consent to participate in the study by signing an informed consent form with good compliance;	
⑧ Non-pregnant and lactating patients;	
⑨ Passing the chemotherapy-related indicators;	
⑩ Those who have no allergic reaction to the ingredients in the formula.	

TBIL: Blood bilirubin, AST: aspartate aminotransferase, CREA: creatinine, WBC: white blood cell count, PLT: platelet count, HCT: erythrocyte pressure, PS: Performance status.

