2.2 Method of administration

Chemotherapy regimen selection: chemotherapy regimens will be selected according to NCCN guidelines, and patients will be treated with platinum-based chemotherapy according to one of the following regimens for 3 weeks each for 4 cycles: (1) NP regimen: vincristine, 25mg/m² on day 1, cisplatin, 75mg/m² on day 1; (2) GP regimen: gemcitabine, 1,250mg/m² on days 1 and 8, and 75mg/m² on day 1; (3) DP regimen: docetaxel, 75 mg/m² on day 1 and cisplatin, 75 mg/m² on day 1; (4) AP regimen: pemetrexed, 500 mg/m² and cisplatin, 75 mg/m² on day 1; and (5) TC regimen: paclitaxel, 200 mg/m² on day 1 and carboplatin, area under the curve (AUC) 6 on day 1, and patients intolerant of cisplatin will be given area under the curve (AUC) 5-6 on day 1 (AUC) 5-6 given carboplatin. All chemotherapeutic agents will be administered intravenously in both groups. The chemotherapeutic agents were administered strictly according to the appropriate instructions and NCCN guidelines for recommended dosage, duration and usage.

For oral administration of traditional Chinese medicine, each bag was soaked in 400 ml of boiling water at 100°C for 20 minutes, divided into 2 portions, each with a content of 200 ml. 200 ml was taken orally twice a day, in the morning and in the evening.

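### Inclusion criterion 5 asks for essentially normal laboratory values, but its own numeric limits for creatinine, bilirubin, platelets and haematocrit lie well outside normal, and no other criterion gives a figure that settles entry

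*Protocol*

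**What the plan says.** Five places in the Protocol bear on the laboratory state a patient may have at entry.

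- **Section 1.2, inclusion 5.** The words require "Patients with basically normal blood and biochemical indicators" and a patient "without organ failure and serious" heart disease. The bracket that follows gives total bilirubin below 68 µmol/L, "AST <90 IU/L, CREA <350" µmol/L, white cells between 3.5 and 12 × 10⁹/L, platelets above 80 × 10⁹/L and haematocrit above 0.20.
- **Section 1.2, inclusion 6.** Besides the performance-status limit, there must be "no other serious comorbidities". No laboratory value is given.
- **Section 1.2, inclusion 9.** In full: "Passing the chemotherapy-related indicators". It names no indicator and no value.
- **Section 1.2, exclusion 5.** It bars "Combined heart, lung, brain, liver, kidney and haematopoietic system and other serious diseases, psychiatric patients". No threshold is given.
- **Section 2.2.** Both arms receive four cycles of a platinum-based regimen, with carboplatin for those who cannot tolerate cisplatin. It adds: "The chemotherapeutic agents were administered strictly according to the appropriate instructions and NCCN guidelines for recommended dosage, duration and usage".

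Two other sections make the entry state matter. Section 2.7.1 names red cells, haemoglobin, creatinine, urea nitrogen and liver function as the changes to watch. The Statistical Analysis section makes meeting the enrolment criteria the first condition for the per-protocol set.

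**The concern.** The only laboratory numbers in the eligibility table disagree with the words they sit beside. Take a patient with creatinine 340 µmol/L, bilirubin 60 µmol/L and haematocrit 0.21, and the other bracketed tests in order. This patient passes every number in inclusion 5, yet could hardly be described as having essentially normal blood and biochemistry, and may well have the kind of kidney, liver or blood disease that exclusion 5 bars. An investigator who works from the numbers and one who works from the words have each followed part of the table.

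Two things are at stake. The first is safety: the open limits concern the same organ systems that section 2.7.1 flags, in patients who all go on to platinum-based chemotherapy. The second is the per-protocol set: if inclusion 5 disagrees with itself, whether such a patient met the enrolment criteria has no clear answer.

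**Working it through.** The Protocol states no derived figure here, so there is nothing to reproduce. The check is how far each bracketed limit lies from normal, and whether another criterion supplies a number that would decide.

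**Inputs from the Protocol (section 1.2):** the six bracketed limits and the age range 18 to 75.

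**Assumptions, because the Protocol gives no reference ranges or body weights:** weight 50 to 80 kg; the reference limits in the table below; 88.4 µmol/L per mg/dL for creatinine and 17.1 for bilirubin.

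**Step 1. Units.** Creatinine 350/88.4 = 3.96 mg/dL. Bilirubin 68/17.1 = 3.98 mg/dL.

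**Step 2. Renal function at the creatinine limit.** Cockcroft-Gault: (140 − age) × weight / (72 × creatinine in mg/dL), times 0.85 for women. The denominator is 72 × 3.96 = 285.1.

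- Highest: man, 18 years, 80 kg: 122 × 80 / 285.1 = 34.2 mL/min.
- Lowest: woman, 75 years, 50 kg: 65 × 50 × 0.85 / 285.1 = 9.7 mL/min.
- Middle: 60 years, 65 kg: 80 × 65 / 285.1 = 18.2 mL/min for a man; × 0.85 = 15.5 for a woman.

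CKD-EPI 2021, which needs no weight, gives 21.5 mL/min/1.73 m² for a man of 18 and 11.3 for a woman of 75. The two formulas agree that renal function at the limit is severely or markedly reduced at every eligible age.

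**Step 3. Each limit against assumed reference limits.**

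| Test | Protocol limit | Assumed reference limit | Limit ÷ reference |
|---|---|---|---|
| Creatinine (µmol/L) | <350 | upper 84 to 133 | 4.2 to 2.6 |
| Bilirubin (µmol/L) | <68 | upper 20 to 26 | 3.4 to 2.6 |
| AST (IU/L) | <90 | upper 35 to 45 | 2.6 to 2.0 |
| Platelets (× 10⁹/L) | >80 | lower 100 to 150 | 0.80 to 0.53 |
| Haematocrit | >0.20 | lower 0.35 to 0.40 | 0.57 to 0.50 |

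The white-cell range of 3.5 to 12 × 10⁹/L is near normal. Haematocrit 0.20 corresponds to haemoglobin of roughly 67 g/L if haemoglobin in g/dL is taken as one third of the haematocrit in per cent (20/3 = 6.7 g/dL).

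The conclusion for creatinine, bilirubin, platelets and haematocrit is the same at both ends of every assumed range.

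**Step 4. Does another criterion decide?** Inclusion 6 and exclusion 5 depend on the word serious and give no threshold. Inclusion 9 gives neither test nor value. Section 2.2 refers outward to drug instructions and guidelines and states no entry limit. So the bracket in inclusion 5 holds the only laboratory limits written in the Protocol.

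**The case against.** **The criteria are cumulative.** A patient must meet every inclusion criterion and no exclusion criterion. The example patient would also have to get past the words of inclusion 5, inclusions 6 and 9, and exclusion 5. This stands. A reader might infer that the table admits patients with severe organ impairment, or that two sites are bound to decide differently. The Protocol does not support either statement: it leaves the decision to whichever wording a site applies.

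**The bracket may define only the organ-failure clause.** It follows that clause, after a semicolon, so the near-normal requirement could be a separate and stricter condition. This is possible but does not remove the problem. The bracket includes white cells, platelets and haematocrit, which belong with the blood indicators of the first clause. And if the first clause does stand alone, it has no number at all.

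**Conflict with the chemotherapy.** A reader might go further and infer that these limits are incompatible with the regimens in section 2.2. That would rest on drug instructions and guidelines that are not part of the Protocol, which itself names no laboratory value as a bar to any regimen. All that can be said is that the limits are not visibly aligned with section 2.2, and that its commitment to follow the instructions may act as a further safeguard.

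**Not every limit is loose.** This stands for white cells, and largely for AST.

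**Randomisation protects the safety comparison.** A concurrent placebo arm on the same chemotherapy background, with tests before treatment, does allow the arms to be compared despite abnormal starting values. So bias between arms is not claimed; the concern is who is exposed and who counts as eligible.

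**Conclusion.** The inconsistency is real and lies first of all within one criterion. Inclusion 5 asks for essentially normal values and then writes limits at 2.6 to 4.2 times an assumed upper reference limit for creatinine, 2.6 to 3.4 times for bilirubin, and 53 to 80% and 50 to 57% of an assumed lower limit for platelets and haematocrit. At the creatinine limit, estimated clearance is about 10 to 34 mL/min over the eligible ages. These sizes rest on the assumed reference ranges and weights; the direction does not change within them.

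The same numbers sit badly with exclusion 5, and inclusion 9 cannot settle the matter because it is empty of values. The consequence is ambiguity over entry, with a bearing on patient safety and on membership of the per-protocol set, which is the secondary efficacy population. The full analysis set is defined by randomisation, dosing and a post-dose assessment, so its membership does not turn on this point, and no effect on the primary disease-free survival result is shown. The Protocol gives no basis for estimating how many patients would fall in the disputed range.

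**What to change.** Reconcile the wording and the numeric limits of inclusion 5 with inclusion 9, exclusion 5 and section 2.2, so that one consistent set of limits decides entry. In particular:

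- state which clause of inclusion 5 the bracket defines, and make words and numbers agree;
- either name the indicators and values meant in inclusion 9 or refer from it to the reconciled limits;
- make clear how exclusion 5 relates to those limits;
- apply the same limits when judging enrolment compliance for the per-protocol set.

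The values and their source are for the sponsor's clinicians to choose; none is proposed here.

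The cost is an amendment to the eligibility table. No new test is needed: inclusion 5 already requires every measurement in its bracket, and section 2.6.3 already schedules routine blood tests and liver and kidney function before treatment. If patients have already been enrolled, their baseline values should be checked against the reconciled table and any affected cases documented before unblinding.
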